The results at 2 years will be the most important goal of the study, on which the main clinical results will be built. The neurophysiological results can be analyzed and presented after the 6-month follow up.

Power calculation

Totally 150 patients will be included, 75 in each treatment group. The study size has been calculated with power 80% and $\alpha = 0.05$ as well as an ability to detect 12 units (SD19) of difference in the ODI, giving 40 follow-up patients in each group. Experience from previous registry-based RCTs within Swespine, regarding loss to follow-up and cross-over (ie patients admitted to non-surgical treatment who wish to switch to surgical intervention), is taken into account. According to this, the loss is considered to be low (<5% after 2 years) [Försth]. In previous studies, this proportion was comprised of 9 to 40% of the conservatively treated patients [Weinstein] [Malmivaara]. Loss to follow-up and cross-over are estimated to be up to 50%, which leads to 75 patients needed in each group.

Each year, 100-130 patients who meet the inclusion criteria are operated at the Department of Orthopaedics (Uppsala University Hospital and + Enköping Hospital). We estimate that 150 patients will be recruited to the study within a period of 24 months.

Flow-chart

Recruitment	The patient is recruited during an outpatient visit to a surgeon. Oral and written information about the study is given.
ICF	The patient gives oral and written consent. The consent is documented in the patient journal and the written consent is filed in the study document binder.
Baseline data	- PROMs via Swespine Study - 6MWT

	
 - Scoliosis standing digital X-rays (AP and lateral views) - ENG/EMG - Blood samples for analysis of inflammatory markers (OLINK)
Randomization	Simple block randomization to the two treatment arms.
Treatment arms	
A. Decompression. Central decompression of the stenotic segments with undercutting of the lateral recesses, free mobilization, and routine follow-up postoperatively by physiotherapist.
 
B. Non-surgical treatment. Exercise on exercise bike according to the "Östersund model" [Nord] 30 min, 3 times/week for 4 months.

Follow-up 6 months	
 - PROMs via Swespine Study - 6MWT - Scoliosis standing digital X-rays (AP and lateral views) - ENG/EMG - Blood samples for analysis of inflammatory markers (OLINK)

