Cross-over	Feasibility for cross-over from group B till A after 6-month follow-up.
Follow-up 1,2 years	
 - PROMs via Swespine Study - 6MWT
Follow -up 5 years	
 - PROMs via Swespine Study

In the treatment group A, in conjunction with the surgical procedure, ligamentum flavum will be collected (which is routinely removed during the decompression surgery) and will be examined with histological methods regarding proinflammatory markers and nociceptors. An 1x1 cm tissue piece will be dissected and saved. The ligament samples will be examined by immunohistochemistry and with proteomics analysis. Proteomics analysis will be performed in collaboration with Olink Uppsala (www.olink.com) where 92 inflammation-related factors will be investigated. Sample management will be in accordance with the Ethics Examination Act of Human Research (2003: 460) and according to the rules of Uppsala Biobank.

References

Försth P, Michaëlsson K, Sandén B.

Does fusion improve the outcome after decompressive surgery for lumbar spinal stenosis?: A two-year follow-up study involving 5390 patients. *Bone Joint J.* 2013 Jul;95-B(7):960-5. doi: 10.1302/0301-620X.95B7.30776.

Försth P, Ólafsson G, Carlsson T, Frost A, Borgström F, Fritzell P, Öhagen P, Michaëlsson K, Sandén B.

A Randomized, Controlled Trial of Fusion Surgery for Lumbar Spinal Stenosis. *N Engl J Med.* 2016 Apr 14;374(15):1413-23. doi: 10.1056/NEJMoa1513721.

Sigmundsson FG, Jönsson B, Strömqvist B.

Outcome of decompression with and without fusion in spinal stenosis with degenerative

spondylolisthesis in relation to preoperative pain pattern: a register study of 1,624 patients. *Spine J.* 2015 Apr 1;15(4):638-46. doi: 10.1016/j.spinee.2014.11.020.

Malmivaara A, Slätis P, Heliövaara M, Sainio P, Kinnunen H; Finnish Lumbar Spinal Research Group.
Surgical or nonoperative treatment for lumbar spinal stenosis? A randomized controlled trial. *Spine (Phila Pa 1976).* 2007 Jan 1;32(1):1-8.

Weinstein JN, Tosteson TD, Lurie JD, Tosteson AN; SPORT Investigators.
Surgical versus nonsurgical therapy for lumbar spinal stenosis. *N Engl J Med.* 2008 Feb 21;358(8):794-810. doi: 10.1056/NEJMoa0707136.

Strömqvist B, Fritzell P, Hägg O, Jönsson B, Sandén B; Swedish Society of Spinal Surgeons.
Swespine: the Swedish spine register : the 2012 report. *Eur Spine J.* 2013 Apr;22(4):953-74. doi: 10.1007/s00586-013-2758-9.

Delitto A, Piva SR, Moore CG, Fritz JM, Welch WC.

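### The sample size treats cross-over as drop-out; if cross-overs gain most of the surgical benefit, 75 per group falls short of 80% power in the upper part of the cited 9–40% range

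*Protocol*

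**What the plan says.** The Power calculation section aims for 80% power at α = 0.05 with "an ability to detect 12 units (SD19) of difference in the ODI", "giving 40 follow-up patients in each group". It then makes an allowance from two sources. For loss to follow-up, "the loss is considered to be low (<5% after 2 years"). For cross-over, defined there as patients allocated to non-surgical treatment who want to switch to surgery: "In previous studies, this proportion was comprised of 9 to 40% of the conservatively treated patients". The two are merged: "Loss to follow-up and cross-over are estimated to be up to 50%, which leads to 75 patients needed in each group". The 12 points are not changed.

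Two other places matter. The Follow-up section sets the main time point: "The results at 2 years will be the most important goal of the study, on which the main clinical results will be built". The Flow-chart has a cross-over row placed after the 6-month visit: "Feasibility for cross-over from group B till A after 6-month follow-up". Its later rows continue patient-reported outcomes at 1, 2 and 5 years, and no rule removes patients who have crossed over.

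**The concern.** Drop-out and cross-over harm a trial in different ways. A patient lost to follow-up contributes no 2-year ODI, so dividing n by one minus the loss rate is right. A group B patient who has surgery after 6 months still contributes a 2-year ODI, now reflecting surgery. Compared as randomised, that patient stays in group B and pulls its mean towards group A. The expected difference falls and n does not. Power depends on the square of the difference but only on the first power of n, so the two allowances are not interchangeable. Cross-over is also defined in one direction only, yet the allowance is applied to both groups.

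The 6-month comparison comes before cross-over is permitted. The 2-year comparison, which carries the main result, is the one exposed. The Background section itself gives heavy cross-over in earlier studies as a reason why the value of surgery is still uncertain. If cross-over is high here and the 2-year result is null, a reader would be told that the sample size had allowed for it.

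**Working it through.** **Inputs from the protocol.** Difference 12, SD 19, α 0.05 (taken as two-sided, which reproduces the stated n), power 80%, 75 per group, loss below 5%, cross-over 9–40% of the non-surgical group.

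**Assumptions made here.** Comparison as randomised; unadjusted two-sample t-test (noncentral t); 12 points is the effect without cross-over; loss exactly 5%, so 75 × 0.95 = 71.25, taken as 71 per group. The share g of the surgical benefit that cross-overs gain is not in the protocol and is varied.

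**1. The protocol's 40.** The t-test needs 40.3 per group for 12/19 at 80% power. The stated 40 reproduces.

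**2. The step from 40 to 75.** As a pure drop-out allowance, 50% requires 40/(1 − 0.5) = 80 per group. Conversely, 75 allows for 1 − 40/75 = 46.7%. A literal 50% drop-out from 75 leaves 37.5 per group and 77% power. This gap is small.

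**3. Cross-over as dilution.** With cross-over rate c, the expected 2-year difference is 12 × (1 − c × g). For example, c = 0.40 and g = 1 give 12 × 0.60 = 7.2 points; g = 0.75 gives 12 × 0.70 = 8.4; g = 0.5 gives 12 × 0.80 = 9.6. Each range below runs between two variance assumptions: a common SD of 19 (higher power), and a group B variance of 19² + c(1 − c)(12g)², which allows for the mixture of patients who did and did not cross over (lower power).

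| Cross-over c | Benefit share g | Difference | Power, 71 per group |
|---|---|---|---|
| 9% | 1 | 10.92 | 92.1–92.5% |
| 24% | 1 | 9.12 | 79.7–81.1% |
| 25% | 1 | 9.00 | 78.6–80.0% |
| 40% | 1 | 7.20 | 59.1–61.1% |
| 40% | 0.75 | 8.40 | 73.3–74.4% |
| 40% | 0.5 | 9.60 | 84.4–84.8% |

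A simulation with the mixture (40,000 runs, g = 1) gave 92.0%, 79.8%, 78.4% and 58.7% at 9, 24, 25 and 40% cross-over, in line with the lower ends.

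**4. Where power falls to 80%.**
- g = 1: cross-over of 23.7–25.0%.
- g = 0.75: 32.2–33.4%.
- g = 0.5: 49.1–50.1%, beyond the cited range.
- At 40% cross-over, the break-even share is g = 0.61–0.63.
- At 40% cross-over and g = 1, the underlying effect detectable with 80% power is 15.0–15.6 points, not 12. Keeping 12 would need 117–122 enrolled per group.

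**5. Other readings.**
- If 12 is already the diluted, as-randomised difference, cross-over needs no allowance. Then 40.3/0.95 = 42.4, so 43 per group would do, and 71 per group gives 96% power.
- If cross-overs were excluded at 40%, the comparison is 71 against 71 × 0.6 ≈ 43, with 90% power, but the groups are no longer those formed by randomisation.

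Both readings give ample power, but neither explains a 50% allowance applied to both groups.

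**The case against.** The strongest reply is that the shortfall rests on choices the protocol does not make. It names no analysis set, and a statistical analysis plan not shown here may fix one. It gives no benefit share and does not say that 12 points is the undiluted effect. With half the benefit, or with 12 read as the as-randomised difference, power exceeds 80% throughout the cited range. Raising n from 40 to 75 already absorbs about 25% dilution.

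All of that is true, and it makes the shortfall conditional. It does not repair the printed calculation, which claims without condition that 75 covers cross-over by taking it off n. Subtraction is the matching arithmetic only if cross-overs are excluded, and that gives up randomisation.

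Baseline adjustment is a fair second point, since ODI is collected at baseline. At 40% cross-over and full benefit it raises power to 71–74% if the baseline correlation is 0.5 and to 77–80% if it is 0.6. With three quarters of the benefit and a correlation of 0.5 it gives up to about 86%, which removes that shortfall. These correlations are assumed and the protocol's calculation uses none, but any restated figures should be labelled as unadjusted.

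The objection that 80 against 75 is trivial also stands. The cited 40% plus 5% gives 40/0.55 = 73, which 75 covers. The conclusion does not depend on that gap.

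**Conclusion.** The concern holds. The protocol treats cross-over as lost patients, although its own definition, the timing of cross-over and the continued follow-up mean that it dilutes the main 2-year difference. The plan is adequate in the lower part of the cited range: power is 92–93% at 9% cross-over even with full benefit. It drops below 80% above about 24–25% cross-over with full benefit, or about 32–33% with three quarters, and reaches 59–61% and 73–74% respectively at 40%. If cross-overs gain less than about 61–63% of the benefit, there is no shortfall in the cited range. These figures assume an unadjusted comparison as randomised, SD 19, 5% loss and an undiluted effect of 12 points. The arithmetic is certain; whether power will in fact be short depends on a cross-over rate and a benefit share not yet known. This should be corrected, but it does not call the trial's design into question.

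**What to change.** In the Power calculation section, separate loss (below 5%, taken off n) from cross-over (9–40%, taken off the difference), and replace the sentence saying that 75 per group covers both up to 50%. State whether the 12 points are before or after dilution by cross-over. If before, text along these lines would do:

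> With 75 per group, 5% loss, SD 19 and 12 points as the effect without cross-over, the unadjusted comparison as randomised at 2 years has 80% power up to about 24% cross-over if patients who cross over gain the full surgical benefit, and up to about 32% if they gain three quarters. At 40% cross-over, power is about 60% with full benefit, 73% with three quarters and 84% with half.

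If the planned analysis adjusts for baseline ODI, the adjusted power can be added with the assumed correlation stated.

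The cost is one reworded paragraph. Enrolment, follow-up and the cross-over rule stay as they are. The stated power becomes less favourable, and the sponsor has to declare an assumption about benefit in cross-overs that the protocol does not now contain.

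### A 50% allowance for loss and cross-over does not lead from 40 evaluable patients to 75 per group: it leads to 80, and 75 covers at most 46.7%

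*Protocol*

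**What the plan says.** The Protocol, section Power calculation, plans 150 patients, 75 per group. The target is a 12-unit difference in ODI with SD 19, at 80% power and alpha 0.05, "giving 40 follow-up patients in each group".

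The section then discusses attrition in two parts:

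- Loss to follow-up: "the loss is considered to be low (<5% after 2 years)".
- Cross-over, defined as "patients admitted to non-surgical treatment who wish to switch to surgical intervention". In previous studies "this proportion was comprised of 9 to 40% of the conservatively treated patients".

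It concludes: "Loss to follow-up and cross-over are estimated to be up to 50%, which leads to 75 patients needed in each group".

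The Flow-chart, row Cross-over, foresees switching in one direction only: "Feasibility for cross-over from group B till A after 6-month follow-up".

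**The concern.** The closing sentence is the only link between the 40 patients the calculation requires and the 75 per group to be enrolled. It presents 75 as the consequence of a 50% allowance, yet halving 75 leaves fewer than 40. If so, the sample size rests on a tolerance it does not meet, and a reader would overestimate how much cross-over the trial can absorb. That matters here because the Background names a large proportion of cross-over as a reason why earlier trials left the question open.

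The sentence also does not say which group the 50% applies to. The loss of power depends on that.

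**Working it through.** **Inputs** (Protocol, Power calculation): difference 12, SD 19, alpha 0.05, power 80%, 40 evaluable per group, 75 enrolled per group, combined allowance 50%, loss under 5%, cross-over 9 to 40% of the conservatively treated. Sidedness is not stated. I take two-sided, because it reproduces the stated 40 (one-sided gives 31).

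**1. The plan's 40.** n per group = 2 × [SD × (z0.975 + z0.80) / difference]² = 2 × [19 × (1.960 + 0.842) / 12]² = 39.35, rounded up to 40. This reproduces. With the t distribution the result is 40.3, that is 41.

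**2. The step from 40 to 75 at 50%.** The number to enrol is n / (1 − d).

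- From 40: 40 / 0.50 = 80.
- From the unrounded figure: 39.35 / 0.50 = 78.7, that is 79.
- From the t-test figure: 41 / 0.50 = 82.
- By the common mistake n × (1 + d): 40 × 1.5 = 60.

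None of these gives 75.

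**3. What 75 does tolerate.** 1 − 40/75 = 0.467, so at most 46.7% combined. At 50%, 75 × 0.50 = 37.5, so 37 or 38 remain.

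**4. What the cited components need.** 5% + 40% = 45%, and 40 / 0.55 = 72.7, that is 73. If the two rates are multiplied, 40 / (0.95 × 0.60) = 70.2, that is 71. At 45%, 75 × 0.55 = 41.25, so 41 remain. The figure of 75 covers the cited rates.

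**5. Power.** Cross-overs are assumed to be left out of the analysis, as the n / (1 − d) inflation implies. The normal approximation is Φ{12 / [19 × √(1/n1 + 1/n2)] − 1.960}. The t-test figure uses the noncentral t distribution.

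| Situation | Evaluable, surgical vs non-surgical | Power, normal | Power, t-test |
|---|---|---|---|
| Target | 40 vs 40 | 80.6% | 79.7% |
| 50% lost in each group | 37 vs 37 | 77.5% | 76.4% |
| 50% lost in each group, unrounded | 37.5 vs 37.5 | 78.1% | 77.0% |
| 50% lost in each group | 38 vs 38 | 78.6% | 77.6% |
| 45% lost in each group | 41 vs 41 | 81.6% | 80.7% |
| 50% lost in non-surgical only, 5% in surgical | 71 vs 37 | 87.6% | 87.0% |
| 50% lost in non-surgical only, 5% in surgical | 71 vs 38 | 88.1% | 87.6% |

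The 71 is 75 × 0.95 = 71.25, rounded down. With 50% lost in each group (37.5 vs 37.5), the drop from the target is 80.6 − 78.1 = 2.5 points (normal) or 79.7 − 77.0 = 2.7 points (t-test).

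**The case against.** The strongest reply accepts the arithmetic and disputes its weight.

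- **Cross-over runs one way.** Both the Power calculation and the Flow-chart describe switching only from non-surgical treatment to surgery, and loss is put below 5%. On those definitions the surgical group has no route to 50% attrition, so the 77% case does not arise. The realistic comparison is about 71 vs 37 or 38. Its information equals 75 × 2 / (1/0.95 + 1/0.50), about 49 per group, which is above 40. On this reading 75 is more than enough for 80% power, and 80 is not needed. This stands, and it limits the consequence. It does not make the sentence correct: the non-surgical group still falls to 37 or 38, below the 40 required in each group, and 75 still does not follow from 50%.
- **The 50% is a loose ceiling above cited rates totalling 45%.** It is true that 75 covers 45%. But the sentence uses the 50% as the figure from which 75 is derived, and a stated ceiling is the case that the sample size should cover.
- **Excluding cross-overs is an assumption.** This also stands. The protocol schedules follow-up after the switching point and does not say that cross-overs drop out. If they are analysed as randomised, cross-over dilutes the difference, and neither 80 nor 46.7% is the relevant figure. The analysis population may be set in an analysis plan that is not at hand. The check here takes the protocol's own approach, which adds cross-over to loss and treats both as lost patients.

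**Conclusion.** The concern holds. Forty evaluable patients and a 50% allowance give 80 per group, not 75, and 75 per group supports at most 46.7%. No standard variant of the inflation step yields 75.

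The error is confined to the stated tolerance and its derivation. The 40 is right, and 75 is adequate for the attrition rates the protocol cites. At the stated 50%, a group ends 2 or 3 patients short of 40. Power falls by about 2.5 points only if both groups lose that share. If the loss is confined to the non-surgical group, with 5% in the surgical group, power stays at about 87–88%.

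These power figures assume a two-sided test and cross-overs excluded from the analysis. Dilution under analysis as randomised is a different question and is not counted here. The sentence should be corrected because the sample size rests on it, but it gives no reason to change enrolment.

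**What to change.** Keep 75 per group and correct the sentence. Suggested wording: *Loss to follow-up and cross-over combined are estimated to be up to about 46% in [the non-surgical group / each group]. With 75 patients enrolled per group, at least 40 evaluable patients then remain in each group, with cross-overs counted as not evaluable.* The check is 75 × 0.54 = 40.5. The figure also has support in the protocol itself, since the cited maxima add to 45%. The phrase *at least 40* stays true for the surgical group if only the non-surgical group loses patients through cross-over.

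Alternatively, keep 50% and state what it gives: 37 or 38 evaluable and about 77% power if it applies to each group, or about 71 vs 37 or 38 and about 87–88% power if it applies to the non-surgical group only, with 5% loss in the surgical group. In either case, name the group or groups.

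The cost is one reworded sentence and a slightly less favourable stated tolerance or power. Recruitment and conduct do not change.
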